6.5. Participant Follow-up

6.5.1. Quarterly Phone Calls

After the Baseline Visit participants will be contacted by phone on a quarterly basis. Using an event ascertainment form, these calls will assess whether a participant has had an exacerbation episode within the last three months. Participants will not be contacted by phone when the timing of a quarterly follow-up coincides with an in-person visit. These contacts will provide a count of self-reported exacerbations within the SPIROMICS population.

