4.1.1.2. Clinically Identified Pulmonary Exacerbation without Hospitalization

During routine follow-up calls and clinic visits, participants will also be queried about their COPD-related antibiotic use, visits to the emergency department, and contacts with their physician. Because of the volume and nature of the records relating to these visits, these records will not be reviewed by the site investigators. These patient reports will provide a count of the number of exacerbations that did not require hospitalization.

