6.7.2. Exacerbations

6.7.2.1. Definition

An acute exacerbation of COPD will be defined as "a sustained worsening of the patient's respiratory condition, from the stable state and beyond normal day-to-day variation, that is acute

in onset." Acute exacerbations will be graded according to the following scale:

1. Mild (requiring home management, with or without contacting a health care provider)
2. Moderate (requiring a visit to a health care provider or Emergency Department but not requiring hospitalization)
3. Severe (requiring hospitalization)

Patients will be queried at every point of contact regarding mild, moderate, and severe exacerbations and regarding the type of treatment received for each exacerbation, in particular antibiotics and/or steroids. Source documentation will be requested for severe exacerbations only (see below).

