6.7.2.2. Hospitalizations

At all scheduled visits and during follow-up interviews, participants will be asked to identify any hospitalizations that have occurred since the last contact. Medical records associated with a self-reported hospitalization play a vital role by providing outside, professional assessment of a participant's health status. In particular, these records serve to identify or verify exacerbations. When a participant reports an admission to the hospital, the study coordinator will ask the participant to release the medical records from that visit for review. Records from all hospitalizations will be obtained by the local site and sent to the GIC for abstraction and review by the Morbidity and Mortality Committee.

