6.7.2.3. Emergency Department Visits and Unscheduled Office Visits

Emergency Department Visits and Unscheduled Office Visits will be considered together as location of care, for these types of services may differ regionally. At all scheduled visits and during follow-up interviews, participants will be asked to identify any Emergency Department visits or unscheduled office visits that have occurred since the last contact. Participants will also be queried as to whether they were treated with antibiotics, steroids, or both as part of a scheduled office visit or received any new medical diagnoses. The purpose of these queries will be to determine whether a COPD exacerbation has occurred or notable comorbidity developed. Cardiac comorbidity and the development of cancer will be of key interest. It is at the discretion of the local PI or designated CoI whether medical records need to be obtained in order to verify occurrence of an exacerbation or notable comorbidity. Medical records related to Emergency department visits or office visits that do not result in a hospitalization will not be submitted to the GIC for abstraction and will not be adjudicated.

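### Exacerbations are collected under two look-back windows and two record-verification rules that do not agree, so the count can have gaps or overlaps and can differ by site

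*Protocol*

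**What the plan says.** **Look-back.** Section 6.5.1 states that "these calls will assess whether a participant has had an exacerbation episode within the last three months", and adds that these contacts will yield a count of self-reported exacerbations. Section 6.7.2.2, which covers all scheduled visits and follow-up interviews, says "participants will be asked to identify any hospitalizations that have occurred since the last contact". Section 6.7.2.3, with the same coverage, says "participants will be asked to identify any Emergency Department visits or unscheduled office visits that have occurred since the last contact". Section 6.7.2.1 adds that "Patients will be queried at every point of contact regarding mild, moderate, and severe exacerbations", without naming a window.

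**Records for events without hospitalization.** Section 4.1.1.2 says "these records will not be reviewed by the site investigators". Section 6.7.2.1 says "Source documentation will be requested for severe exacerbations only". Section 6.7.2.3 says "It is at the discretion of the local PI or designated CoI whether medical records need to be obtained in order to verify occurrence", with reference to both exacerbations and notable comorbidity. It also keeps these records out of central abstraction and adjudication.

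**Role of the count.** Section 7.4.3 names exacerbations among the primary clinical endpoints, and 7.4.1 plans Poisson regression for them.

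**The concern.** One telephone interview is given two recall periods. Time that no question covers cannot be recovered at analysis. Time covered twice can put the same episode in the count twice unless events are dated and matched. Section 6.5.1 also asks whether an episode occurred, although its stated product is a count.

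The verification rules cannot all be followed. A site that relies on 4.1.1.2 would leave self-reports as they are. A site that relies on 6.7.2.3 could check some of them. With no central adjudication of these events, no later step brings the sites back to a common standard. What is at stake is whether a primary clinical endpoint is complete and comparable across sites.

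**Working it through.** **1. The plan's own figure.** Section 7.1 assumes annual rates of 1.0 (Mild/Moderate, 1,500 participants) and 1.5 (Severe, 600), 92% retention, a Poisson likelihood ratio test and two-sided alpha of 0.05, and states power above 95%.
- Retained: 1,500 × 0.92 = 1,380 and 600 × 0.92 = 552.
- Simulation of that test (20,000 runs, one or three years of exposure): power about 100%.
- Hand check, one year: SE of the log rate ratio = √(1/1,380 + 1/(552 × 1.5)) = 0.044; ln(1.5)/0.044 ≈ 9.2.
- With negative-binomial dispersion of 2 (assumption), one year: SE = √((1 + 2)/1,380 + (1/1.5 + 2)/552) = 0.0837; power = Φ(0.4055/0.0837 − 1.96) = 99.8%.

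The stated power reproduces, and reconciling the rules does not change it.

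**2. When the windows differ.** Take a quarter as 91 days.

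| Days between contacts | Not covered by a three-month question | Covered twice |
|---|---|---|
| 49 | 0 | 42 |
| 70 | 0 | 21 |
| 91 | 0 | 0 |
| 112 | 21 (19% of the interval) | 0 |
| 133 | 42 (32% of the interval) | 0 |

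Uneven spacing is built into the protocol. Visits replace calls that coincide with them (6.5.1), a visit may run over 42 days (6.3), and the six-week wait after an exacerbation also applies when the Year 1 to 3 visits are scheduled (5.3.1.2). Spacing can therefore depend on the event being counted.

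**3. Missed contacts.** Assume 12 quarterly contacts over three years, each missed independently with probability m. The documents give no value for m.
- Literal three-month rule: each missed contact loses its quarter, so capture = 1 − m.
- Since the last contact: only an unbroken run of misses at the end of follow-up is lost, so capture = 1 − (m + m² + … + m¹²)/12.

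| m | Three-month rule | Since the last contact |
|---|---|---|
| 5% | 95% | 99.6% |
| 10% | 90% | 99.1% |
| 20% | 80% | 97.9% |
| 30% | 70% | 96.4% |

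**4. Which events the three-month rule governs.** Under the 6.7.2.1 grading, severe events are hospitalizations, which 6.7.2.2 covers. Moderate events are provider or emergency visits, which 6.7.2.3 covers; it also asks about antibiotics or steroids given at scheduled office visits. Mild events are managed at home and fall under neither, so 6.5.1 holds the only window stated for them.

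**5. Verification.** If some sites checked records and removed a share v of self-reports (assumption), their count would be 1 − v times that of a non-checking site with the same true rate: 0.90 at v = 10% and 0.60 at v = 40%. The protocol gives no v and does not say that unconfirmed reports are removed. The figures show only what differing practice could do.

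**The case against.** The strongest reply is that sections 6.7.2.2 and 6.7.2.3 already ask since the last contact at every visit and follow-up interview, so nearly all moderate and severe events are covered. This stands, and it confines the look-back problem mainly to mild events. The windows also coincide when contacts are on schedule. The event form, a manual of procedures or the SAP may contain clearer wording or a rule for removing duplicates, so actual double counting is not shown.

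A reader might infer that the planned rate ratio of 1.50 would shrink because sicker participants miss more contacts. With 10% missed in Mild/Moderate and 20% in Severe, a literal three-month rule for all events gives (1.5 × 0.80)/(1.0 × 0.90) = 1.33. The documents do not support this as an expected effect: they say nothing about missed contacts by severity, 7.1 assumes equal 92% retention, and most of the events concerned are asked about since the last contact. Under that wording the same assumptions give (1.5 × 0.979)/(1.0 × 0.991) ≈ 1.48.

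A reader might also infer that discretionary verification is steered by knowledge of the phenotype under test. Novel subgroups are still to be discovered (7.1), so a local investigator may know the severity stratum but not those subgroups. Sections 4.1.1.2 and 6.5.1 both describe the product as a count of participant reports. Hospitalized events are unaffected, because 4.1.1.1 and 6.7.2.2 agree on obtaining the records and reviewing them centrally.

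**Conclusion.** Both conflicts are in the current protocol text, concern a primary clinical endpoint and should be reconciled. The look-back conflict creates a risk of gaps and overlaps, chiefly for mild events, of unknown size. The contrast of 95% to 70% against 99.6% to 96.4% rests on assumed missed-contact rates of 5% to 30%, independent misses and a literal reading of 6.5.1, and applies only to events that 6.5.1 alone governs. The verification conflict means that counts of non-hospitalized events can depend on site practice; whether and by how much they would is not stated. The stated power is not in error, and no direction of bias between severity strata is established.

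**What to change.** - **Section 6.5.1:** ask for the number and dates of exacerbations since the last completed contact, matching 6.7.2.2 and 6.7.2.3. Dates let overlapping reports be recognised.
- **Section 6.7.2.3:** remove local discretion for verifying exacerbations only, and keep it for notable comorbidity, which the same sentence covers.
- **Counting rule:** at all sites, count mild and moderate events by self-report under the existing 6.7.2.1 grading, as 4.1.1.2 and 6.5.1 already describe. No treatment-based criterion for moderate events is needed. Use any records obtained only for a sensitivity analysis.

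The cost is a change to the event form and two protocol sentences. The drawback is that unverified self-reports stay in the count, but uniformly across sites.

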6.6. Safety and Adverse Events

6.6.1. Participant Safety

It is expected that some participants will experience changes in disease severity, will develop comorbidities to COPD, and/or will expire during the course of participating in SPIROMICS. SPIROMICS staff will provide appropriate referrals for medical care if during study visits clinically relevant changes in disease status are found. SPIROMICS is not a treatment trial and as such will not report the above listed events as adverse or serious adverse events as they are considered the natural progression of COPD.

Adverse events that result directly from study procedures, including those risks outlined in each procedure section and any not listed in this document, will be reported to the Steering Committee and OSMB.

6.6.1.1. Procedures for Serious Adverse Events

The FDA (2009) defines a serious adverse event as an adverse event that:

- Results in the participant's death,
- Is life-threatening,
- Results in Hospitalization (initial or prolonged),
- Results in significant, persistent, or permanent change, impairment, damage, disruption, or disability in the participant's body function/structure, physical activities or quality of life,
- Results in a congenital anomaly, or
- Requires Intervention to Prevent Permanent Impairment or Damage.

If a serious adverse event (SAE) occurs during a study visit the study coordinator should first insure the participant receives any needed medical attention. If the study coordinator is notified by phone, the coordinator should confirm that the participant has received medical attention. The study coordinator should then notify the site Principal Investigator and complete the Adverse Event form found in on the study website. For serious adverse events the study coordinator should submit the form to the GIC within 48 hours of learning of the event. Study coordinators should comply with local regulations and policies when notifying the institutional IRB.

The GIC will notify the Project Officer, Steering Committee, and Observational Studies Monitoring Board within 48 hours of receiving the initial event notification.

6.6.1.2. Procedures for Adverse Events

Adverse events are undesirable experiences resulting from participation in the SPIROMICS study (FDA, 2009). Common adverse events are listed in the risks section of each procedure.

If an adverse event (AE) occurs during a study visit the study coordinator should first insure the participant receives any needed medical attention. If the study coordinator is notified by phone,

the coordinator should confirm that the participant has received medical attention. The study coordinator should then notify the site Principal Investigator and complete the Adverse Event form found in MOP 1. For adverse events the study coordinator should submit the form to the GIC within seven days of learning of the event. Study coordinators should comply with local regulations and policies when notifying the institutional IRB.

The GIC will notify the Project Officer, Steering Committee, and Observational Studies Monitoring Board within a week of receiving the initial event notification.

6.6.2. Measures to Protect the Participant

Some of the procedures performed during a SPIROMICS have known potential risks. A number of safety measures are in place to minimize these risks. During the baseline interview participants will be screened for conditions that might increase their risk while participating in these procedures, including history of heart disease, heart failure, or recent myocardial infarction. In addition, clinical center staff will discuss the risks associated with each of these procedures with participants during the screening process and before each procedure begins.

If a participant experiences a condition requiring immediate medical attention, such as a cardiac event, angina, acute hypertension the research physician will be consulted immediately and the visit terminated.

6.6.2.1. Emergencies

In the event of a life-threatening emergency a participant will require immediate transport to an acute care facility however clinical center staff may need to implement some emergency measures prior to transport. Many minor emergencies will require only onsite treatment.

6.6.2.2. Major Emergencies

Each clinical center will establish procedures for handling major medical emergencies including plans for how to transport a participant to the nearest medical facility. These procedures will define:

- 1) Who is in charge during an emergency
- 2) Who is to administer treatments
- 3) Who is to be notified
- 4) What action clinic staff is to take
- 5) Which reports are to be filed

Clinical centers will have access to either a physician, physician's assistant, or a registered nurse any time a participant is being interviewed or participating in a procedure. Each center has, in addition to trained personnel and emergency equipment, the phone numbers for police and fire stations, ambulance services, and specific phone numbers or codes to alert medical teams (if applicable) posted in conspicuous places. In each participant's record contain contact information for his or her primary care physician, home or work numbers, and one or more emergency contacts.

6.6.2.3. Minor Emergencies

Minor emergencies are those not requiring emergent medical care, and can be handled at the clinical center. Common minor emergencies include syncope and dyspnea and clinic staff is trained in the appropriate response. While a minor emergency may not require physician care, study staff is to alert the research physician present to the event.

6.6.2.4. Reporting

All emergencies, major or minor, are documented. Documentation includes completing institutionally approved forms identifying the emergency as well as reporting the event to the Project Office and GIC. This form is to be completed by the person in charge at the time of the emergency, and all reports are co-signed by the clinic physician.

6.7. *Clinical Endpoint Ascertainment*

6.7.1. All cause mortality

6.7.1.1. Death report during follow-up call

Death is an endpoint of interest that will be analyzed as part of this phenotyping protocol. The opportunity to assess vital status will naturally occur during regularly scheduled study visits and follow-up phone calls. During the course of routine follow-up contact, if the study coordinator learns from a proxy that the participant is deceased, the coordinator should offer condolences and request that the proxy provide information regarding the circumstances of the participant's death. Records pertaining to a participant's death will be requested and sent to the GIC. Data will be reviewed and cause of death assigned to one of the following causes: respiratory, cardiovascular, cancer, other. The data will then be reviewed by at least two members of the Morbidity and Mortality Committee not associated with the institution where the death occurred and a final cause of death assigned according to the Principles of Adjudication. If the two committee members disagree on cause of death, a third member of the committee will review death records and cause of death will be assigned based on majority consensus.

6.7.1.2. National Death Index

The National Death Index will be annually searched to determine if any participants lost to follow-up have died. If a participant is found on this list, the death certificate and any associated hospitalization records will be requested, and the Death CRF submitted. The National Death Index will also be queried at the completion of the study.

6.7.2. Exacerbations

6.7.2.1. Definition

An acute exacerbation of COPD will be defined as "a sustained worsening of the patient's respiratory condition, from the stable state and beyond normal day-to-day variation, that is acute

in onset." Acute exacerbations will be graded according to the following scale:

1. Mild (requiring home management, with or without contacting a health care provider)
2. Moderate (requiring a visit to a health care provider or Emergency Department but not requiring hospitalization)
3. Severe (requiring hospitalization)

Patients will be queried at every point of contact regarding mild, moderate, and severe exacerbations and regarding the type of treatment received for each exacerbation, in particular antibiotics and/or steroids. Source documentation will be requested for severe exacerbations only (see below).

6.7.2.2. Hospitalizations

At all scheduled visits and during follow-up interviews, participants will be asked to identify any hospitalizations that have occurred since the last contact. Medical records associated with a self-reported hospitalization play a vital role by providing outside, professional assessment of a participant's health status. In particular, these records serve to identify or verify exacerbations. When a participant reports an admission to the hospital, the study coordinator will ask the participant to release the medical records from that visit for review. Records from all hospitalizations will be obtained by the local site and sent to the GIC for abstraction and review by the Morbidity and Mortality Committee.

6.7.2.3. Emergency Department Visits and Unscheduled Office Visits

Emergency Department Visits and Unscheduled Office Visits will be considered together as location of care, for these types of services may differ regionally. At all scheduled visits and during follow-up interviews, participants will be asked to identify any Emergency Department visits or unscheduled office visits that have occurred since the last contact. Participants will also be queried as to whether they were treated with antibiotics, steroids, or both as part of a scheduled office visit or received any new medical diagnoses. The purpose of these queries will be to determine whether a COPD exacerbation has occurred or notable comorbidity developed. Cardiac comorbidity and the development of cancer will be of key interest. It is at the discretion of the local PI or designated CoI whether medical records need to be obtained in order to verify occurrence of an exacerbation or notable comorbidity. Medical records related to Emergency department visits or office visits that do not result in a hospitalization will not be submitted to the GIC for abstraction and will not be adjudicated.

6.7.3. Lung Transplantation

Lung transplantation is also an endpoint of interest that will be analyzed as part of this protocol. During the course of routine follow-up contact, if the study coordinator learns that the participant has undergone a lung transplant, the study coordinator will ask the participant to release the medical records from that hospitalization which will be submitted to the GIC along with the Hospitalization CRF.

7. Statistical Plan

7.1. Sample Size and Power

Thirty-two hundred (3,200) participants will be recruited and enrolled at six clinical centers into four strata (non-smokers, smokers, mild/moderate COPD, severe COPD) as illustrated in Table 1. The sample size requirements for the study are to (1) provide an adequate number of adverse clinical events (e.g., exacerbations, all-cause mortality) over three years of follow-up and (2) sufficient precision in estimating decline in FEV₁ over three years of follow-up in order to support the study objectives of discovering novel, homogeneous subgroups of COPD and identifying potentially useful, intermediate outcomes of disease progression.

Table 1. SPIROMICS Enrollment Strata

	Non-Smokers (Stratum 1)	Smokers (Stratum 2)	Mild/Moderate COPD (Stratum 3)	Severe COPD (Stratum 4)
Smoking Status	< 1 pack-year	> 20 pack-years	> 20 pack-years	> 20 pack-years
Bronchodilator Status for Assessing Lung Function	Pre- bronchodilator	Post- bronchodilator	Post- bronchodilator	Post-bronchodilator
FEV1/FVC ratio criteria	FEV1/FVC > .7	FEV1/FVC > .7	FEV1/FVC < .7	FEV1/FVC < .7
Other Lung Function Criteria	FVC>LLN	FVC>LLN	FEV1 > 50% pred.	FEV1 < 50% pred.
Sample Size	N = 200 (6.25%)	N = 900 (28.13%)	N = 1500 (46.88%)	N = 600 (18.72%)

Data on event rates for all-cause mortality in the COPD population are available from the TORCH study, a clinical trial comparing salmeterol plus fluticasone propionate versus placebo and each therapy alone over a three-year period (Calverley, et al., 2007). Below we use the TORCH results to provide a lower bound on plausible differences between hypothetical subgroups of COPD patients with respect to morbidity/mortality for purposes of estimating power. In addition, where possible, estimates of FEV₁ change over time are derived from published findings for power analyses. Estimates of the power available for comparisons of the Mild/Moderate versus Severe COPD enrollment strata are provided for illustration purposes, as sizes of novel subgroups yet to be discovered are unknown at this time. All statistical tests will be two-sided, with Type I error alpha=0.05 after controlling for multiple testing.

For the TORCH study, all-cause, three-year mortality rates ranged from 15.2% among placebo patients to 12.6% in the combination therapy group. Results from Anthonisen et al. (1986) found

that the three-year mortality was approximately 25% for patients with FEV₁ in the range 30%-39% , and approximately 13% for those with FEV₁>50%. More recently Celli et al. (2004) reported approximately 18% three-year mortality for patients with FEV₁>36% and 30% for patients with FEV₁<36%. We conservatively power the SPIROMICS study to detect a difference in all-cause mortality, assuming a 15% rate for Severe patients versus 10% for Mild/Moderate patients. With 1,500 patients in the Mild/Moderate COPD stratum vs. 600 patients in the Severe COPD stratum, we will have 88% power for this comparison.

For the TORCH study, the annual rate of exacerbations was 1.13 per participant for placebo versus 0.85 for combination therapy. In a computer model of COPD progression based on literature surveys, Borg et al. (2004) assumed an average annual rate of moderate to severe exacerbations of approximately 1.05 among COPD patients with GOLD status I/II, and a rate of 2.05 for exacerbations among COPD patients with GOLD status III. We conservatively power the SPIROMICS study to detect a difference in annual exacerbation frequency between the Mild/Moderate and Severe COPD strata, assuming an annual rate of 1.0 in the Mild/Moderate COPD stratum vs. a rate of 1.5 in the Severe COPD stratum. Using simulation and assuming a simple Poisson log-likelihood ratio test for difference in individual counts of exacerbations in the two strata and assuming 92% retention in both strata, we obtain power in excess of 95% to detect the differences.

For decline in FEV₁, the TORCH study found differences in change from baseline FEV₁ values of 0.092 (L) between the combination therapy group and placebo (95% CI = [0.075, .108]) (Calverley et al, 2007). With the proposed disease severity subgroup sample sizes and assuming attrition due to mortality ranging from 10% in the Mild/Moderate stratum to 15% in the Severe stratum, and 92% retention in those surviving in each strata, we would have approximately 95% power to detect a difference of 0.20 times the standard deviation in FEV₁ change from baseline values (using a two-sample t-test on baseline vs. Year 3 FEV₁ in the two strata).

From the earlier conservative mortality assumptions, we expect 240 (11%) or more all-cause mortality events among the 2100 COPD patients during the course of SPIROMICS. For tests of direct association of potential surrogate endpoints/markers with this outcome, we consider for simplicity a dichotomized surrogate endpoint with relative frequency 0.50 for each value of the surrogate. In order for surrogate endpoint to demonstrate promising utility for further prospective validation in the context of a clinical trial, we propose that the surrogate confer an odds ratio of 1.8 or more. The correlation structure of the potential surrogates is not known a priori, so we use a significance level of 0.001 in order to account for multiplicity of testing (corresponding to a Bonferroni correction for 50 tests). Under these assumptions and assuming retention of 92%, a contingency table test of mortality vs. the surrogate will have 77% power to reject the null hypothesis.

7.2. *Interim Study Progress Reports*

7.2.1. *Steering Committee Reports*

Monthly management reports are prepared by the GIC and provided to the Steering Committee for monitoring of study progress. Tables and figures summarizing enrollment, completion of study procedures and visits, and baseline characteristics are included.

